Subjects will be told that the purpose of the study is to evaluate the effects of medications on human behavior related to mood, sleep, and substance abuse (cocaine users). Information about the components of the experimental procedure will be explained. Details of the random assignment procedure (placebo or active dose) will be explained. Subjects will be informed of their attendance expectations. Other information on the consent form will include a full description of study requirements, reimbursement, risks, benefits, alternatives, and the role of the local IRB. All questions will be answered before written consent is requested. All research conducted in our laboratory and the CNRA has prior approval from the Committee for the Protection of Human Subjects (CPHS) of the University of Texas Health Science Center - Houston.

E5. Potential Benefits of the Proposed Research to the Subject and Others

All services provided in these studies will be free. The studies should help compliment and advise clinical research focused on stopping cocaine use, preventing relapse, and improving cognitive and behavioral functioning related to impairment following cocaine abuse. Subjects will be told if unusual information is discovered during the study that will make a difference in treatment for this or other

problems. By taking part in this research subjects may help themselves toward recovery and others with similar problems.

Subject Payment. The payment schedule is detailed below. Subjects will be paid the medication compliance, study visit bonus, and participation earnings at the end of each experimental day (M, W, F). Subjects will receive an additional bonus (\$50) for completing of the study. Total possible payment for meeting all study requirements and collecting all bonus payments will be \$337.

Medication compliance. \$2 for each metric: 1) Medical Event Monitoring System (MEMS) bottle opening, (2) pill counts (empty bag), (3) positive riboflavin markers, and (4) text reply to reminder. Absence of each will result in payment not be earned for that specific metric. Total possible payment = \$8 per day X 14 study days = \$112. **Study visit bonus.** \$10 for on time arrival and providing an alcohol-free breath sample and urine sample. Total possible payment = \$10 per day X 7 visit days = \$70. **Participation.** Total possible payment = \$15 per day X 7 visit days = \$105. **Completion bonus** \$50.

E6. Importance of the Knowledge to be Gained.

Research participation may assist non-treatment seeking subjects in abstaining from cocaine during study, and via study completion protocol, bring them into contact with treatment resources at our research center and in the community. Cocaine dependence is marked by repeated relapse, leading to devastating consequences on a personal and societal level. Currently, there is no medication that has been shown to be broadly effective in reducing cocaine use. Suvorexant (and orexin agonists more broadly), may help reduce sleep disruptions and anxiety, and attenuate craving and biased attention toward drug cues – helping to reduce risk of relapse. This experiment will compliment and provide valuable information to our ongoing and future addiction work, and contribute to the knowledge base in the treatment of cocaine dependence. Our procedures have been designed to minimize the probability of risks. Our research center has an excellent track record in conducting human psychopharmacology experiments and clinical trials with the utmost attention to safety.

E7. Inclusion of Women and Minorities

Women, minorities, and children will be included at minimum to the extent they are reflected in this cocaine-dependent population. In previous cocaine clinical studies at the Treatment Research Clinic (TRC), the percentage of females and males is approximately 20% and 80% respectively. We will continue recruitment efforts to achieve a 50-50 balance and thus permit meaningful analyses by sex across groups. One effort will be to have the TRC outreach coordinator present educational material and referral information at women's clinics in Houston and the surrounding communities. In the past this has helped to enhance recruitment of women with cocaine dependence.

The ethnic representation has been 67% Black, 25% White, and 8% Hispanic. In the absence of data on the prevalence of cocaine dependence disorder in the Houston area, we cannot define ethnic base rates. The medical center environment is not known to be uniquely avoided by any particular ethnic group and patients view it as favorable and neutral. Nevertheless, we are prepared to implement recruitment procedures to ensure a more diverse patient population. These procedures include: 1) Targeted advertising in newspapers which serve minority communities (e.g., Hispanic or Latino communities). 2) Distribution of flyers and notices in neighborhoods known to have a high minority population. 3) Engaging in outreach activities on an ongoing basis, e.g., contacting church and community leaders in the Hispanic communities to provide educational material about cocaine dependence and its consequences; providing contact information to aid in referrals to our clinic (see **Core** for additional details).

E8. Inclusion of Children

Children (age 18-21years) will be included in this research. The incidence of severe cocaine abuse/dependence is relatively small in the population of youth less than 18 years old. From a safety perspective, risks of exposure to the proposed study medication in substance-dependent children have not been established. The safety and efficacy of the proposed study medication should be established in adults first, before conducting this type of treatment research in children.

E9. Data and Safety Monitoring Plan (NIH/NIDA specific issues)

1. The Principal Investigator will be responsible for knowing the policies of the local IRB (the UT – Houston Committee for the Protection of Human Subjects, CPHS). The PI will adhere to CPHS policies and maintain accurate documentation of CPHS correspondence and reports (e.g., annual report). The PI is responsible for documentation and handling of all possible study-related adverse events. The Treatment Research Clinic (TRC) within our Center for Neurobehavioral Research on Addictions (CNRA) has longstanding data collection and safety monitoring systems in place that will be available for the proposed study. These include staff training, weekly audit of data collection/entry, medical screening with results reviewed by on-site nurse and physician, use of standardized assessments, continued medical monitoring during the study, procedures to monitor medication compliance (MEMS caps, texts). As PI, [name] will assure that the above systems are in place and functioning properly during the study.

2. A Monitoring Committee will provide additional, independent oversight of data related to subject safety. This committee will perform the following activities: (a) review the research protocol and plans for data and safety monitoring; (b) evaluate study progress, including data quality, participant recruitment rates, retention rates, outcome and adverse experience data, and risk versus benefit profile; (c) make recommendations to the PI for a discontinuation of study medication for an individual patient based on adverse experiences; (d) make recommendations to terminate the study because of safety concerns; and (e) protect the confidentiality of the data and the results of monitoring. The Committee will be blind to study medication, unless they believe that termination of the trial is warranted. This committee meets annually to review all CNRA studies, and this present study will be added to the DSMB review in 2016. The DSMB report is submitted annually to CPHS.

3. Adverse events (AE) will be reported to the UT-CPHS on an annual basis. Serious adverse events will be reported immediately (verbally within 24 hours) to the UT-CPHS, the Monitoring Committee, and to the NIDA. A written report will follow as soon as possible but in no more than three days. The written report will be in the format required by the local IRB and will contain information regarding the date of the AE, description of the AE, severity rating (Grade 1 to 4), assessment of cause, whether the AE indicates an increased risk for current or future subjects, and whether changes to the informed consent form are necessary.

4. We will also use an ongoing Adverse Event Log (AEL) based on NIDA SAFTEE procedures. The AEL will record the duration, severity, and frequency or any adverse events, signs, and symptoms. An evaluation will be made as to the event's relationship to the study drug(s), scaled as unrelated, unlikely, possible, and probable. The AEL will be included in the report to DSMB.

E10. Specific Issues: NIDA / NACDA Guidelines on Administration of Drugs to Human Subjects.

Risk/Benefit. These issues are described in sections **E1 through E6**. As noted above, the potential for advances in scientific and treatment domains related to addiction are considerable. Based on the qualifications and long history of work in this area by the investigative team and the careful screening and monitoring for subject safety, we feel there is a favorable balance of potential benefit against risk.

Data Safety Monitoring Board is described in **E9**.

Informed Consent is described in section **E4**.

Subject Selection is described in section **E1**.

Confidentiality is described in section **E4**.

Medical and Psychological Screening and Services are described in sections **E1, E4, and E9**, as well as sections **D1 and D2** of the application.

Administration of Drugs to Individuals Who Have Never Used Drugs. Study drugs will not be

administered to subjects who have never used drugs. By definition all subjects will be individuals with substance use disorder (cocaine). Most of our subjects with cocaine use disorders also have an extensive history of use of other illicit drugs.

Involvement of Individuals Currently Addicted to Drugs and/or Are Frequent Drug Abusers. We have taken into consideration the need to assess the participant's ability to provide informed consent (via use of screening and the Shipley-2 aptitude assessment). While these are non-treatment seeking individuals, a serious and concerted effort will be made to link these individuals to drug abuse treatment. At study end, subjects will receive a follow up medical examination and a session with a licensed counselor in our treatment research clinic, who will provide information about treatment options and referrals. As described thoroughly in D1, D2, E1 and E4 we have rigorous medical examination and screening procedures to assure the absence of any medical or mental condition for which further drug exposure would be contraindicated. Our procedures do not entail exposure to higher doses, rates of administration, or new route of administration than they would normally encounter by under usual circumstances. If subjects have participated in prior clinical drug intervention trials at our treatment research clinic, a complete list of drugs and dosing protocols will be reviewed and kept in his/her evaluation record. Subjects using any current CNS active medications will be excluding from testing and rescheduled (if medication use was idiosyncratic, e.g., OTC for recent cold or headache) or excluded (if medication use is regular or for a chronic condition). In particular, we will exclude those with alcohol use disorders or who report frequent alcohol consumption (> 7 time drinks per week), as suvorexant is contraindicated with alcohol due to potentially dangerous interactions with regard to sedative effects.

Administration of Drugs to Incarcerated Individuals. Individuals who are currently on parole or probation with random drug testing by court officers, or who are currently incarcerated, will be excluded

Administration of Drugs to Individuals with Mental Disorders. Individuals with DSM-IV Axis - I mental disorders other than SUD will be excluded.

Drug Doses and Routes of Administration. The proposed doses in these experiments (10 mg, 20 mg) have all been safely given to human subjects in previous laboratory experiments and clinical trials. Standard routes of administration (PO capsules) will be used. No doses will be given outside the range of those already administered to humans in previous studies and indicated in the prescribing information in the investigator's brochure.

Prior and Current Drug Treatment Status. All subjects in the proposed experiments will be non-treatment seeking. Although appropriate measures for help with addiction will be provided at study end, where subjects will receive a follow up medical examination and a session with a licensed counselor in our treatment research clinic, who will provide information about treatment options and referrals.

Prior and Current Treatment Experience. If subjects have participated in prior clinical drug intervention trials at our treatment research clinic, a complete list of drugs and dosing protocols will be reviewed and kept in his/her evaluation record. Subjects using any current CNS active medications will be excluding from testing and rescheduled (if medication use was idiosyncratic, e.g., OTC for recent cold or headache) or excluded (if medication use is regular or for a chronic condition).

Women of childbearing potential will not be excluded from these experiments.

Pregnant Women will be excluded from these experiments, and urine pregnancy testing will be performed at each visit to the research center (3 to 5 days per week).

Special Considerations Across the Lifespan. Individuals under the age of 19 will be excluded from this research due to risks and unknown effects of these drugs in adolescents, and ethical concerns of administering drugs of abuse to individuals this age. Additionally, individuals this age may be in school,

which would preclude the normal daytime participation time. We will also exclude individuals over age 55, as elderly subjects also constitute a vulnerable population with regard to drug effects. Additionally, changes in anatomy and physiology in the elderly that may alter the metabolism and short and long-term effects of drugs, compromising both safety and scientific validity.

Study Personnel Training and Experience. All medical and psychiatric screening and interviews will be conducted by trained clinicians, who are first trained by experienced SCID interviewers using standardized training videotapes from Biometrics Research, NY. All personnel associated with this grant have successfully completed ethics training in the Protection and Welfare of Human Participants, and certification is on file at the Health Science Center CPHS and office of sponsored projects. CNRA pharmacists will carry out preparation of medication; distribution of medication by research assistants will follow after training has been conducted by the PI ([name]).

Infection Risk Reduction Counseling and Testing. As described in sections D1, D2, E1 and E4, we recognize these risks and have included the necessary tests and precautions for disease transmission and infection risk (HIV, tuberculosis (TB), hepatitis, syphilis). HIV counseling will be made available as deemed appropriate by medical personnel in the treatment research center.

Safety of Research Participants Outside of the Research Site. These issues are addressed in section E4. They are repeated here for clarity. In addition to the screening criteria for inclusion, each visit to the laboratory will include a full side effects profile. Additionally, subjects will be evaluated for signs of impairment or side effects, first by a research assistant and then by a PI and CNRA research nurse. The assessment battery includes subjective questionnaire, nystagmus, touching nose, balance, and walking a straight line. If the subject is determined to be unimpaired, s/he will be released promptly. If any signs of sedation or other impairment are detected, participants will be required to remain at the experimental site until such symptoms are no longer observed. In the event of either an unexpected adverse event or heavy sedation, we have several measures in place. First, [name] (CNRA medical director) is a licensed MD with clinical experience and training in emergency medicine. Thus, a physician will be in the immediate vicinity of laboratory. Offices and clinical space are contiguous to the lab. Second, Ben Taub Hospital, a level 5 emergency medical center is located less than 5 minutes away from our building. Finally, in the event of extended sedation or impairment, in which any subject does not appear clear-headed, feeling well, and in full control of his or her behavior, two steps will be taken. First, the subject will remain in the lab until such time that the PI, medical director, or research nurse deems that it is safe for him or her to leave (e.g., passing the test described above). Second, if necessary, we will arrange for a taxi service to drive the subject back to his/her home.

The following procedures will be taken to safeguard against adverse medication events: (1) careful initial intake evaluation to determine eligibility based on inclusion/exclusion criteria (including exclusion for alcohol use disorder or frequent regular use); (2) thorough physical evaluation prior to treatment, consisting of physical examination, standard laboratory tests, electrocardiogram, toxicology screen, pregnancy test and vital signs; (3) repeated tests during treatment; (4) daily monitoring of pill taking using MEMS caps, returned pill counts, and self-report; (5) weekly review of adverse events and medication compliance; (6) evaluation by the study physician ([name]). Specific criteria will be used to exclude potential subjects for whom any of the study medications is contraindicated. Any abnormal physiological, psychological, or behavioral event will be evaluated and, if indicated, will result in the subject's removal from the study.

For this project, we will use an Adverse Event Log (AEL) based on NIDA SAFTEE procedures. The AEL will record the duration, severity, and frequency of any adverse events, signs, and symptoms. An evaluation will be made as to the event's relationship to the study drug, scaled as unrelated, unlikely, possible, and probable. The AEL will be included in the report to DSMB. Relevant information is also included in section E9.

Referral to Treatment. As noted above, at study end subjects will receive a follow up medical examination and a session with a masters-level licensed counselor or RN in our treatment research

clinic, who will provide information about treatment options and referrals. If depression or suicidal ideation is measured at risk during the study, participation will be terminated and appropriate referrals made (see above).

Incomplete Disclosure. We have no elements of deception in this project, other than withholding of dose information to subjects about dose contents on days of testing (e.g., suvorexant or placebo). However, informed consent documents will contain full disclosure of the drug that may be received during the course of the experiments, along with potential side effects. No information about study risks will be withheld from subjects.

Payment for Participation in Research. Subjects will be paid daily for attendance and for performance on the behavioral tasks, and a bonus at the end of the study for completion. Subjects will be paid the medication compliance, study visit bonus, and participation earnings at the end of each experimental day (M, W, F). Subjects will receive an additional bonus (\$50) for completing of the study. Total possible payment for meeting all study requirements and collecting all bonus payments will be \$337. Medication compliance. \$2 for each metric: 1) Medical Event Monitoring System (MEMS) bottle opening, (2) pill counts (empty bag), (3) positive riboflavin markers, and (4) text reply to reminder. Absence of each will result in payment not be earned for that specific metric. Total possible payment = \$8 per day X 14 study days = **\$112.** Study visit bonus. \$10 for on time arrival and providing an alcohol-free breath sample and urine sample. Total possible payment = \$10 per day X 7 visit days = **\$70.** Participation. Total possible payment = \$15 per day X 7 visit days = **\$105.** Completion bonus **\$50.**

F. Vertebrate Animals

Not applicable.

References

- 1 SAMSHA. SAMHSA's latest report on the nation's mental health. *Psychiatr Serv* **63**, 619, doi:10.1176/appi.ps.20120p619 (2012).
- 2 SAMHSA. Results from the 2012 National Survey on Drug Use and Health: Summary of National Findings. NSDUH Series H-46; Substance Abuse and Mental Health Services Administration, Rockville, MD. HHS Publication No (SMA) 13-4795. (2013).
- 3 Mena, G. *et al.* Cocaine-related health emergencies in Europe: a review of sources of information, trends and implications for service development. *Eur Addict Res* **19**, 74-81, doi:10.1159/000341719 (2013).
- 4 SAMHSA. Vol. NSDUH Series H-49 (HHS Publication No. (SMA) 14-4887., Rockville, MD, 2014).
- 5 Koob, G. F. & Volkow, N. D. Neurocircuitry of addiction. *Neuropsychopharmacology* **35**, 217-238, doi:10.1038/npp.2009.110 (2010).
- 6 Verrico, C. D., Haile, C. N., Newton, T. F., Kosten, T. R. & De La Garza, R., 2nd. Pharmacotherapeutics for substance-use disorders: a focus on dopaminergic medications. *Expert Opin Investig Drugs* **22**, 1549-1568, doi:10.1517/13543784.2013.836488 (2013).
- 7 Haile, C. N. & Kosten, T. R. Pharmacotherapy for stimulant-related disorders. *Curr Psychiatry Rep* **15**, 415, doi:10.1007/s11920-013-0415-y (2013).

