3. **Sleep interaction:** To characterize the degree to which sleep mediates the effect of suvorexant on drug cue reactivity. We hypothesize an indirect effect of suvorexant on drug cue reactivity via sleep, such that attenuation of cocaine cue reactivity (attentional bias, craving) will be greater in those with larger improvements in sleep duration.

*Conceptual Model:
Orexin System Effects on Relapse Risk*

Figure 1. Summary of Conceptual Model

Research Plan

Our group at the University of Texas Center for Neurobehavioral Research on Addiction (CNRA) has developed, utilized, and validated laboratory models of drug relapse, allowing us to examine pharmacotherapeutic and cognitive-behavioral interventions for relapse prevention.

Study design. To accomplish the project aims, we will utilize a mixed-model experimental design, with a between-groups factor of dose (suvorexant vs. placebo) and a within-subjects factor of time. Subjects will receive suvorexant (**10 mg week 1, 20 mg week 2**) or placebo PO, once daily at 10 PM. Medication condition will be double-blind, with urn-randomized assignment to dose condition balanced by gender and severity of cocaine use. A summary of timelines and measures is shown in the Table below.

Mon	Wed	Fri	Mon	Wed	Fri	Mon
1,4,5,6,7	1,2,3,4,5	1,2,3,4,5	1,2,3,4,5,6,7	1,2,3,4,5	1,2,3,4,5	1,2,3,4,5,6,7
Key: (1) Provide medication (MEMS bottle); (2) Compliance data for medication adherence (MEMS, pill count, riboflavin, text message); (3) Side effects data, med check, UA toxicology; (4) Sleep data; (5) stress /anxiety data; (6) acute stressor challenge (cold pressor); (7) Cue reactivity data						

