Participants and setting. The study will test 30 current cocaine users (enroll 45 to complete 30), 19 to 55 years old, who meet current DSM-5 criteria for cocaine use disorder (CUD) of at least moderate severity (≥ 4 symptoms). Subjects meeting criteria for substance use disorders other than cocaine, marijuana, or nicotine will be excluded. Notably, because the study medication (suvorexant) is contraindicated with alcohol use, we will exclude subjects with alcohol use disorders (via screening at intake). We will also exclude those individuals who are drinking > 10 alcoholic drinks per week (NIAAA criteria problem drinking = at least 14 drinks per week), and who are unwilling to stop using alcohol in the evening for the two weeks of the study. We will exclude those who report binge drinking (NIAAA criteria = in < 2.5 hours, 5 drinks for men, 4 drinks for women).

Other exclusion criteria will include significant and unstable medical/ psychiatric disorders which might make participation hazardous; acute or chronic health conditions; and concomitant medication use contraindicated with the study medication (suvorexant). This will be accomplished via full medical evaluation at intake by [name], M.D., CNRA Medical Director. The study will be conducted at the Neurobehavioral Research Laboratory at the CNRA, directed by [name]. Recruitment strategies will include local advertising in print media, public service announcements on radio, and referrals to CNRA in the Houston metropolitan area. Based on previous and current CNRA recruitment rates of participants with CUD, we expect to enroll 3-4 participants per month to meet recruitment goals.

Measurements

Cue reactivity: Attention bias (AB) task is a saccade-based eye-tracking measurement, developed by [name] to assess attentional bias to drug cues⁴⁸. Eye movements (saccades) have advantages over other variables because they are directly observable, ecologically valid, and typically stable across repeated measures^{49,50}. AB measures utilizing eye movements have produced moderate to robust effects for a broad class abused substances⁵¹⁻⁵³, including cocaine^{34,48,54}. Using our drug specific anti-saccade task, the between-group effect size for anti-saccade error rates in the presence of cocaine cues was large: CUD vs. control Cohen's $d_{av} = 0.6$ ⁴⁸.

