Data Analyses. We will use multilevel modeling to evaluate cue reactivity (attentional bias, craving) as a function of suvorexant, time, and the interaction of suvorexant x time. Hypothesis evaluation will utilize both Frequentist and Bayesian methods. Power and sample size focus on the effect of suvorexant on drug cue reactivity (AB, CCQ). From a Frequentist perspective, assuming a correlation of $r = 0.5$ between measurement points and $\alpha = 0.05$, a sample of $N=30$ participants will provide 80% power to detect a moderate effect (Cohen’s $f = .0.24$) for the interaction if treatment and time. For Bayesian analyses, multilevel priors will be vague and neutral: coefficients ~Normal (mean = 0, variance = 1×10^6), level 1 variance ~ Gamma (shape=.001, scale=.001), level 2 variances ~ Uniform (0,100). Frequentist statistical models will utilize traditional mediation analyses as recommended by Baron and Kenny⁶⁸, which permits unbiased OLS estimates appropriate for this experimental design and sample size⁶⁹, and which we have utilized in previous published research⁷⁰. Bayesian statistical models will utilize path analysis (BSEM) to evaluate the mediating effects of stress/anxiety (biological and subjective-rated) and sleep (biological and subject-rated) for the effects of suvorexant on drug cue reactivity. An example of a mediation analysis using Bayesian SEM may be found Arbuckle⁷¹. Uncertainty surrounding the Bayesian estimate for the indirect effect employs the posterior distribution of the parameter (i.e. the product coefficient): a density denoting the probability that different values of the parameter obtain given the observed data. This approach may be particularly important for evaluating more complex mediation models (e.g. multiple mediators, latent variables) in the context of small sample sizes. Use of the MCMC (Monte Carlo Markov Chain) approach in Bayesian analyses has demonstrated superior small sample performance relative to maximum likelihood-based approaches in continuous, normally distributed data⁷². These properties are likely due to the MCMC approach’s lack of reliance on large sample size assumptions⁷³. BSEM prior specification will adapt recommendations from Muthén and Asparouhov⁷⁴.

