Subject Payment. The payment schedule is detailed below. Subjects will be paid the medication compliance, study visit bonus, and participation earnings at the end of each experimental day (M, W, F). Subjects will receive an additional bonus (\$50) for completing of the study. Total possible payment for meeting all study requirements and collecting all bonus payments will be \$337.

Medication compliance. \$2 for each metric: 1) Medical Event Monitoring System (MEMS) bottle opening, (2) pill counts (empty bag), (3) positive riboflavin markers, and (4) text reply to reminder. Absence of each will result in payment not being earned for that specific metric. Total possible payment = \$8 per day X 14 study days = **\$112**. **Study visit bonus.** \$10 for on time arrival and providing an alcohol-free breath sample and urine sample. Total possible payment = \$10 per day X 7 visit days = **\$70**.

Participation. Total possible payment = \$15 per day X 7 visit days = **\$105**. **Completion bonus \$50**.

Subject participation requirements. Subjects must take the medication as close as possible to 10:00 PM each evening, and reply “yes” to the medication text prompt (texts will be sent at 15-minute intervals from 9:45 PM to 10:30 PM). On M, W, F over 2 consecutive weeks (see Study Design), subjects will visit the lab at 10 AM. At every visit, they will provide the following: medication update (MEMS bottle), side effects data questionnaire, med check up with nurse, UA fluorescence and toxicology, sleep data (wrist monitor and sleep questionnaire), and stress/anxiety questionnaires. The visit will take approximately 1 hour. In addition, on each Monday (day 1, 7, and 14) subjects will complete: (1) the cold pressor test (with cardiovascular measures and saliva sample for cortisol level), (2) the saccade-based attentional bias test, and (3) the cocaine cue reactivity questionnaire. On these three study days, the visit will take approximately 2 hours.

Data Safety Monitoring Plan

E1. Human Subjects Involvement and Participant Characteristics

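### The urn balances on gender and cocaine-use severity, but no planned model includes either factor: a mild loss of precision for between-arm levels, and possible confounding in the mediation regressions

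*Combined protocol and SAP*

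**What the plan says.** All references are to the combined protocol and SAP.

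- **Randomisation** (Research Plan, Study design): "urn-randomized assignment to dose condition balanced by gender and severity of cocaine use". The severity measure, its cut-point and the urn parameters are not given.
- **Multilevel model** (Data Analyses): cue reactivity is evaluated "as a function of suvorexant, time, and the interaction of suvorexant x time". No covariate is named.
- **Mediation** (Data Analyses): Baron and Kenny OLS regressions and Bayesian path models, again with no covariate named. The plan does not say whether levels or changes are analysed.
- **Power** (Data Analyses): the 80% figure is "for the interaction if treatment and time", with 30 participants.
- **Aims** (Hypotheses and Specific Aims): aim 1 carries the label of a main effect; aims 2 and 3 are mediation through stress/anxiety and sleep.
- **Severity and the mediators**: the background section on stress/anxiety associates lifetime stress with cocaine-use severity, and the section on sleep describes a two-way relation between severity and sleep.
- **Sex** (E7): recruitment is meant to allow analyses by sex. That is not a covariate in the planned models.

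**The concern.** Forcing balance on a prognostic factor removes part of the chance difference between arms. A model that omits the factor still counts that variation as error, so its standard errors for a between-arm comparison are larger than the design warrants. The test is then conservative, and precision that the randomisation has secured goes unused. With 30 completers there is little precision to spare.

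The mediation aims raise a separate issue, and there the error runs the other way. Randomisation protects the path from drug to mediator and the total effect, but not the path from mediator to outcome. The protocol itself ties severity to both mediators. If severity also drives cue reactivity, it is a common cause of mediator and outcome, and leaving it out can make a mediator look active when it is not.

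**Working it through.** **1. The plan's own figure.** Inputs from Data Analyses: N = 30, r = 0.5, alpha = 0.05, and f printed with a stray point, read as 0.24 (0.024 would give 5.7% power). There are two arms and three cue-reactivity visits: "on each Monday (day 1, 7, and 14) subjects will complete". For the within-between interaction:

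- lambda = f² × N × m / (1 − r) = 0.0576 × 30 × 3 / 0.5 = 10.37
- df = (2 − 1)(3 − 1) = 2 and (30 − 2)(3 − 1) = 56
- power = 80.8%

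The stated 80% reproduces as the three-visit interaction test. The between-arm main effect at the same f has only 34% power, so it is not the test behind the figure.

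**2. Between-arm comparison of levels (simulated).** N = 30, urn on two binary factors, 30% women (the split anticipated in E1), severity split 50/50 (assumed). R² is the share of subject-mean variance that the two factors explain; it is assumed. The drug difference is set for 80% power at R² = 0: 0.865 outcome SD. The SD of a three-visit mean is √((1 + 2 × 0.5)/3) = 0.816, so this is 0.865/0.816 = 1.06 SD of the subject mean. There were 8,000 runs per cell for type I error and 6,000 for power.

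| R² | Type I error, unadjusted | Power, unadjusted | Power, adjusted |
|---|---|---|---|
| 0 | 4.9% | 79.5% | 77.9% |
| 0.1 | 4.4% | 80.0% | 82.0% |
| 0.2 | 3.8% | 80.8% | 86.0% |
| 0.3 | 3.6% | 81.3% | 90.8% |

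Adjusted type I error was 4.8-5.2% in these rows. Repeat simulations agreed to about half a point on type I error and one to two points on power. With 15 of 45 lost at random ("enroll 45 to complete 30"), unadjusted type I error moves back towards nominal: 4.6% at R² = 0.1 and 4.1% at 0.3.

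**3. The powered suvorexant x time test (simulated).** A stable, additive subject factor cancels from within-subject contrasts. Without the factors, type I error was 4.7-5.1% for R² from 0 to 0.5, and power was 79.9, 80.3 and 80.3% at R² = 0, 0.3 and 0.5. Adding factor x time terms gave 78.5, 78.7 and 78.5%, a cost of about 1.5 points. The test is affected only if the factors predict change over time. When they explain 10 or 30% of the linear change, unadjusted type I error is 4.3 or 3.7%, and factor x time terms move power from 78.3 to 79.3% or from 70.1 to 78.7%.

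**4. Mediator-to-outcome path, levels analysed.** Suppose the true mediator effect is zero and severity correlates rho with both mediator and outcome (assumed). The spurious mediator-outcome correlation within arm is then rho². With N = 30 and arm in the model, the Fisher z statistic is centred on atanh(rho²) × √(30 − 1 − 3):

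- rho = 0.3: atanh(0.09) × 5.10 = 0.46; P(|Z| > 1.96) = 7.5%
- rho = 0.4: atanh(0.16) × 5.10 = 0.82; P(|Z| > 1.96) = 13.0%

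Simulations gave 7.0-8.0% and 12.9-13.6%. With gender and severity in the regression the rate was about 5%. At rho = 0.2 the unadjusted rate was 5.6-5.9%, so the problem is negligible there.

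**The case against.** The strongest reply is that the trial is powered on treatment x time, where additive factors cancel. Cue reactivity on day 1 is measured at a 10 AM visit and the first dose is at 10 PM, so a mean over all three visits includes an untreated baseline. The interaction is then the natural carrier of the drug effect, and the label on aim 1 may only mean direct as opposed to mediated. This stands. A reader might infer that the powered test is itself conservative or underpowered because the factors are missing. The documents do not support that, since nothing in them says gender or severity predicts two-week change.

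The assumed shares can also be called generous. A 30% share split equally needs men and women to differ by √(0.15/0.21) = 0.85 SD and the severity halves by √(0.15/0.25) = 0.77 SD, in a sample already restricted to at least four symptoms. That also stands: 30% is best read as an upper case, and at 10% the gain is about 2 points.

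A reader might further infer that omitting severity undermines the missing-at-random assumption, given the expected dropout. No passage links severity to dropout, and the multilevel model already uses the observed cue-reactivity values, so that argument is not made here.

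The claim that any error is conservative, and hence harmless, holds for the arm comparison. It does not cover aims 2 and 3, where the error can be anti-conservative. If those regressions use change scores, however, an additive severity effect cancels there too.

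**Conclusion.** The gap is real: two factors judged important enough to balance are absent from every planned model. Its effect is conditional. For between-arm comparisons of levels it is a mild loss of efficiency, from nothing at R² = 0 to 9-10 power points at R² = 0.3, and random dropout makes the conservatism smaller. For the powered interaction there is no effect unless the factors predict change. For the mediation regressions on levels, false positives on the mediator-to-outcome path rise to about 8% or 13% at correlations of 0.3 or 0.4.

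A reader might take that last result as proof that the mediation analyses are confounded. The documents link severity to stress and sleep but not to cue reactivity, so it remains a plausible risk.

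The results rest on assumed prognostic strength, urn parameters, a 50/50 severity split and normal outcomes. This is worth correcting because the remedy is cheap; it does not threaten the main test.

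**What to change.** In Data Analyses:

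1. Add gender and baseline cocaine-use severity as fixed effects in the multilevel models, and state the severity measure and coding used in the urn.
2. Add both as covariates in the frequentist and Bayesian mediation equations, and say whether those equations use levels or changes.
3. Add gender x time and severity x time as a sensitivity analysis. Put them in the main model only if the factors are expected to predict change.
4. Keep the unadjusted model as a sensitivity analysis.

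The cost is a few sentences and no new data, since both factors must be known at allocation. If the factors are not prognostic, the between-arm comparison loses about 1-2 power points. Factor x time terms would cost the powered test about the same, taking its error df from 56 to (30 − 4) × 2 = 52. Main effects alone leave the interaction test unchanged.
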